1.2.4.1. Power in Baseline BPH Treatment Subgroups

Although this study will not formally test the treatment effect in subgroups by baseline BPH treatments, it is sufficiently sized to estimate treatment differences within these subgroups. Assuming that approximately half of the subjects are on alpha blockers alone and half on alpha blockers plus 5-ARI per stratified randomization, then approximately 544 subjects will be randomized to each subgroup with 462 evaluable (231 per arm). Using the above assumptions with a two-sided test with a type-I error of 0.10, each subgroup will have 97.1% power for micturition episodes and 94.5% power for urgency episodes. Assuming that the endpoints and subgroups are independent, then the power for each subgroup to be significant on both endpoints is 91.7%, and the power for both subgroups to show significant treatment difference on both endpoints is 84.0%.

1.2.4.2. Urodynamics Substudy

Approximately 75 subjects will be enrolled in the Urodynamics substudy, randomized 1:1 to placebo or vibegron 75mg. Assuming a 20% drop-out rate, 60 subjects will be evaluable, 30 in each treatment arm. Noninferiority margins of -3 mL/second for maximum urinary flow (Qmax) and 15 cm H₂O for detrusor pressure at maximum urinary flow (PdetQmax) from Abrams et al [1] were used to characterize power. Standard Deviation of each parameter was estimated from Nitti et al [2], which used the same noninferiority margins.

Using the noninferiority margins described above and a one-sided test of noninferiority with type-I error of 0.05:

30 evaluable subjects per treatment group provides approximately 97% power against the alternative hypothesis of equality for Qmax assuming standard deviation of 3.2 mL/second.

For PdetQmax, 30 evaluable subjects per treatment group provides approximately 79% power against the alternative hypothesis of equality assuming standard deviation of 23.5 cm H₂O. Assuming independence of these tests and requiring both to be within the non-inferiority margin, the power of the composite outcome is approximately 77%.

2. PLANNED ANALYSES

2.1. Interim Analysis

No interim analysis is planned for this study.

An external independent DSMB will be utilized in the study to ensure external objective medical and/or statistical review of safety issues in order to protect the ethical and safety interests of subjects and to protect the scientific validity of the study.

An external statistician will provide the summaries required to the DSMB. No adjustment to the type I error will be made because there is no efficacy data to be reviewed. The schedule of any planned analysis and analysis plan for DSMB review is described in the charter and separate DSMB SAP.

2.2. Final Analysis

The study consists of two parts: Part 1 (approximately 80 subjects) and Part 2 (approximately 1008 subjects). The two study parts are consistent with respect to the study schedule; the only exception is that Part 1 includes additional orthostatic blood pressure and heart rate measurements up to Week 4 to assess for potential orthostatic changes. Part 2 also contains a urodynamics sub-study (approximately 60 subjects). Thus, all data except for orthostatic blood pressure for Part 1 and urodynamic data from the subgroup of Part 2 will be pooled for analyses.

The production and quality control of all tables, figures and listings will be provided by a clinical research organization (eClinical Solutions, LLC) under the supervision of Urovant Sciences, Inc.

Statistical programming will start after data have been collected and are available in the database. Blinded dry-runs using dummy treatment code will be performed prior to database lock to ensure programming displays and algorithms are developed as planned.

The planned final analysis will be performed once the clinical database lock has taken place and treatment codes have been unblinded.

3. ANALYSIS POPULATION

3.1. Analysis Sets

All analysis sets defined below include subjects from both Part 1 and Part 2 except for the Safety Analysis Set for orthostatic blood pressure for subjects in Part 1, and the Urodynamics Evaluable Set and Per-Protocol Set for Urodynamics which include subjects who participate in the urodynamics sub-study in Part 2 only.

3.1.1. Screened Set

The Screened Set consists of all subjects who are screened for the study. This population is used primarily for subject accounting purposes and will generally not be used for summary or analysis. This set includes all subjects that signed the informed consent form and have screening data entered into the database, including screen failures (subjects who did not receive any run-in treatment), run-in failures (subjects who discontinued after receiving run-in treatment and prior to randomization), and randomized subjects.

3.1.2. Placebo Run-in Set

The Placebo Run-In Set consists of all subjects who receive placebo run-in treatment. Subjects will be considered run-in failures if they receive run-in treatment but are not randomized to receive double-blind medication. Subjects who inadvertently received vibegron during run-in are not included in the placebo run-in set.

3.1.3. Randomized Set

The Randomized Set consists of all subjects who are randomized to receive any double-blind study medication regardless of whether they took a dose or not.

3.1.4. Safety Analysis Set

The Safety Analysis Set will serve as the primary population for the analysis of safety data in this trial. Since Part 1 includes additional orthostatic blood pressure assessments while Part 2 includes an additional sub-study with urodynamics measurements, it is necessary to have separate FAS definitions for these assessments. The following SAF populations are defined in the study:

- **Safety Analysis Set (SAF):** consists of all randomized subjects who receive at least one dose of double-blind study medication. Subjects will be classified according to the treatment they actually received; subjects who receive any dose of vibegron will be classified as vibegron subjects, subjects who receive only doses of placebo will be classified as placebo subjects.
- **Safety Analysis Set for Orthostatic Blood Pressure (SAF – Orth):** a subset of SAF to include all subjects in Part 1 who received at least one dose of double-blinded study medication and have at least one evaluable change from baseline orthostatic blood pressure measurement.

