9.3. Populations for Analyses

Analysis Populations

Screened Set

The Screened Set consists of all subjects who are screened for the study. This population is used primarily for subject accounting purposes and will generally not be used for summary or analysis.

Run-in Set

The Run-in set consists of all subjects who entered the run-in period of the study. Subjects will be considered run-in failures if they enter the run-in period but are not randomized to receive double-blind medication.

Randomized Set

The Randomized Set consists of all subjects who are randomized to receive study medication regardless of whether they take a dose.

Safety Analysis Set (SAF)

The Safety Analysis Set consists of all subjects who receive at least one dose of double-blind study medication. Subjects will be classified according to the treatment they actually received.

Full Analysis Set (FAS)

The Full Analysis Set (FAS) population will serve as the primary population for the analysis of efficacy data in this trial. Since the endpoints related to incontinence only apply to subjects who meet the definition of incontinence at trial entry, it is necessary to have a separate FAS definition with an additional criterion to define the primary analysis population for incontinence endpoints.

FAS consists of all randomized subjects who took at least one dose of double-blind study medication and have at least one evaluable change from baseline micturition measurement. Subjects will be analyzed according to their randomized treatment, irrespective of premature discontinuation, according to the Intent-to-Treat (ITT) principle.

Full Analysis Set for Incontinence(FAS-I)

FAS-I consists of all randomized subjects with incontinence at baseline who took at least one dose of double-blind study medication, have an evaluable baseline urgency urinary incontinence measurement, and have at least one evaluable change from baseline urgency urinary incontinence measurement.

Note that “subjects with incontinence at baseline” are defined as meeting the following criteria:

- An average of ≥ 8.0 micturitions per Diary Day
- An average of ≥ 1.0 urinary incontinence episodes per Diary Day

Per-Protocol Set (PPS) and Per-Protocol Set for Incontinence (PPS-I)

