3.2. Violations and Deviation

Subjects who do not meet eligibility criteria but are still randomized will be analyzed according to the analysis sets described in Section 3.1.

Major protocol deviations are considered to have major impact on subject safety, efficacy or the validity of the study data.

Patients with major efficacy protocol deviations will be excluded from the PPS and PPS-I under the assumption that the deviation may have an impact on the efficacy analysis, and from PPS-UES under the assumption that the deviation may have an impact on the urodynamics analysis. This may include, but is not limited to the following:

- Subjects who do not meet the following inclusion criteria:
 - On a stable dose of alpha blocker
 - Average frequency of ≥ 8 and ≤ 20 micturitions per day in the baseline diary
 - Average frequency of ≥ 3 urgency episodes per day in the baseline diary
 - Average frequency of ≥ 2 nocturia episodes per night in the baseline diary
- Subjects who meet any of the following exclusion criteria:
 - Total 24-hour urine volume output of >3000 mL based on any baseline diary day
 - History of prostate surgery
 - Subject started using diuretics within 28 days prior to screening
 - Nocturnal Polyuria ($> 1/3$ of total urine output per 24 hours occurring at nighttime) assessed on any day of the baseline diary
 - Has received an intravesical or intraprostatic treatment with any botulinum toxin, resiniferatoxin, or capsaicin within 6 months prior to screening
 - Use of any prohibited anticholinergics or beta-3 adrenergic agonists as detailed in protocol section 10.6 within 28 days prior to screening
- Concomitant use of prohibited medications as detailed in protocol section 10.6
- $<70\%$ Investigational Product [IP] compliance from Baseline through Week 12
- Visit delay at or prior to Week 12 causing more than 14 days without IP
- Failed to complete any diary day for an expected Week 12 diary within Study Day 68-102 [PPS and PPS-I only]

Exclusion from per-protocol analysis is noted for each protocol deviation in the Protocol Deviation specifications.

The final list of major protocol deviations will be finalized and documented before database lock except for the deviation of wrong treatment which will be confirmed upon study unblinding. All major protocol deviations related to efficacy will be finalized prior to unblinding. Only major protocol deviations will be summarized and listed in the Clinical Study Report (CSR).

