5.3. Other Baseline Characteristics

The data from the 3-day bladder diary during run-in period (reviewed at Visit 3 Baseline visit) prior to first dose of double-blind medication will be used as baseline for each subject. This includes average number of daily micturition episodes, average number of daily urgency episodes, average number of nocturia per night, average number of daily urge urinary incontinence episodes, and average volume voided per micturition. In addition, the baseline IPSS Storage score, prostate volume, Qmax (maximal urinary flow) at baseline as determined by uroflowmetry (see section 7.7 for details), and baseline post-void residual urine will be presented. These will be summarized by treatment group and overall using descriptive statistics for continuous data for all subjects in FAS, FAS-I, PPS and PPS-I analysis sets.

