7.1. Adverse Events

AEs will be coded using MedDRA version 22.0 or later.

All reported AEs (whether treatment emergent or not) will be included in by-subject AE listings. Sorting will be by country, site, subject, date of event, SOC, PT and then verbatim description.

An AE will be considered treatment emergent (TEAE) if it begins or worsens in severity after the first dose of the double-blind Study Treatment through 5 days after the last dose of Study Treatment or rollover to the extension study, whichever occurs first. Partial AE start dates will be imputed as detailed in [Section 4.2.3](#).

Summary tables will be based on TEAEs. The incidence of TEAEs will be presented using counts and percentages of subjects with TEAEs and tabulated by SOC and PT. SOC will be sorted in descending frequency and PT within SOC will be sorted by descending frequency based on the incidence across subjects overall. If a subject has multiple occurrences (start and stop) of an event associated with a specific SOC or PT within a SOC, a subject will only be counted once in the incidence count for the SOC or PT within SOC respectively.

An overall summary table of AEs by treatment group will be presented detailing the number and percentage of subjects, and number of events for the following categories:

- At least one TEAE;
- At least one Treatment-Related TEAE;
- At least one Grade ≥ 3 TEAE (Mild = Grade 1, Moderate = Grade 2, Severe or Medically Significant = Grade 3, Life-Threatening = Grade 4, Death = Grade 5)
- At least one Grade ≥ 3 Treatment-Related TEAE;
- At least one Serious TEAE;
- At least one Serious Treatment-Related TEAE;
- At least one TEAE leading to Discontinuation from Study Medication;
- At least one TEAE of Special Interest;
- At least one Treatment-Related TEAE of Special Interest

Where not otherwise noted, all the following summaries are presented by PT in descending overall frequency:

- All TEAEs (by SOC and PT in descending overall frequency);
- All TEAEs (by PT in descending overall frequency)
- Treatment-Related TEAEs (i.e., possibly or probably related);
- All TEAEs by SOC, PT, and maximum severity (where the maximum intensity per patient will be counted at each level of summarization);
- TEAES with Grade ≥ 3 ;
- Treatment-Related TEAES with Grade ≥ 3 ;

- Serious TEAEs;
- Treatment-Related Serious TEAEs;
- Fatal TEAEs;
- TEAEs leading to Discontinuation from Study Treatment;
- TEAE of Special Interest;

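### As worded, the SAP's safety classification would count as a vibegron subject a man given vibegron by mistake in run-in who took only placebo after randomisation.

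*SAP*

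**What the plan says.** - **Run-in.** SAP 3.1.2 provides for mistaken vibegron before randomisation: "Subjects who inadvertently received vibegron during run-in are not included in the placebo run-in set". It states no other consequence.
- **Safety set membership.** The Safety Analysis Set (SAF) in SAP 3.1.4 "consists of all randomized subjects who receive at least one dose of double-blind study medication". Vibegron in run-in is no bar to entry.
- **Safety set grouping.** The same bullet then says that "subjects who receive any dose of vibegron will be classified as vibegron subjects" and that "subjects who receive only doses of placebo will be classified as placebo subjects". Neither phrase names a study period.
- **Protocol.** Section 9.3 says only: "Subjects will be classified according to the treatment they actually received". It has no any-dose rule, and SAP Section 9, on changes from the protocol, does not mention one.
- **What is counted.** Under SAP 7.1 an adverse event is treatment-emergent (TEAE) "if it begins or worsens in severity after the first dose of the double-blind Study Treatment". SAP 5.9 measures exposure over the double-blind period.
- **Models.** The safety ANCOVA in SAP 4.2.2 carries one actual-treatment variable. SAP 7.3.1, 7.5, 7.6 and 7.7 apply that model to blood pressure and pulse, PVR, urodynamics and uroflow.
- **Diary baseline.** SAP 5.3 takes "The data from the 3-day bladder diary during run-in period" as baseline. Table 3 sets the window from the first run-in dose to Day -1.
- **Per-protocol exclusions.** The nearest item in SAP 3.2 is "Use of any prohibited anticholinergics or beta-3 adrenergic agonists as detailed in protocol section 10.6 within 28 days prior to screening".

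**The concern.** The label and the data it governs come from different periods. For the man described, the dose that makes him a vibegron subject was taken in run-in, before any event or exposure is counted. Everything that is counted happened on placebo. His placebo experience therefore goes into the vibegron column, and anything that happened to him on the mistaken drug is not a TEAE in either column.

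The misplacement mixes the two groups and so pulls safety comparisons toward no difference. That is the unfavourable direction for a safety table, and for the urodynamics sub-study, which SAP 1.2.4.2 characterises with noninferiority margins.

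A secondary gap concerns efficacy. This man's baseline diary was recorded while he may have been taking vibegron. The SAP makes no exception for such a baseline, and no printed per-protocol item names the case.

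**Working it through.** The plan states no figure on this point, so the check is a trace through the rules followed by a scale calculation.

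**Trace.** Take a man who receives vibegron in run-in, is randomised to placebo and takes only placebo for 24 weeks.

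1. SAP 3.1.2: he leaves the Placebo Run-in Set. Nothing removes him from the SAF or the Full Analysis Set (FAS).
2. SAP 3.1.4, vibegron phrase: he has had a dose of vibegron, so he meets it.
3. SAP 3.1.4, placebo phrase: he has not had only placebo, so he fails it. Both phrases point to vibegron.
4. SAP 7.1 and 5.9: his TEAEs and exposure start at the first double-blind dose, so all of them are placebo data.
5. SAP 4.2.2: the actual-treatment label carries this into the safety models. Listings use planned assignment unless otherwise noted, so they would show him under placebo with no sign of his run-in exposure.

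**Scale in the full SAF.** The planned arm is 544 (SAP 1.2.4). The number of misplaced placebo men, k, is not given; 1 to 20 is an assumption. So are the event rates, 10% on vibegron and 5% on placebo.

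Share of the vibegron column = k / (544 + k). Displayed rate = (544 × 0.10 + k × 0.05) / (544 + k).

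| k | Share | Displayed rate | Fall from 10% (points) |
|---|---|---|---|
| 1 | 1/545 = 0.2% | 54.45/545 = 9.99% | 0.01 |
| 5 | 5/549 = 0.9% | 54.65/549 = 9.95% | 0.05 |
| 10 | 10/554 = 1.8% | 54.90/554 = 9.91% | 0.09 |
| 20 | 20/564 = 3.5% | 55.40/564 = 9.82% | 0.18 |

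With assumed rates of 5% and 2%, the fall runs from 0.01 to 0.11 points.

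**Small sets.** Part 1 has about 80 men randomised 1:1, so 40 per arm, and one man is 1/40 = 2.5%. The urodynamics sub-study plans 30 evaluable men per arm, and one man is 1/30, about 3%.

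**Efficacy.** Suppose, as an extreme, that all k men were in the placebo arm (462 evaluable) and that each on-drug baseline was lowered by the full planned effect (0.46 micturitions, 0.60 urgency episodes). The placebo mean change would shift by k × 0.46/462 = 0.001 to 0.020 micturitions and k × 0.60/462 = 0.001 to 0.026 urgency episodes per day for k = 1 to 20. The error comes before randomisation. If it falls equally on both arms, the expected net shift in the treatment difference is zero.

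**Per-protocol list.** The beta-3 agonist item covers only the 28 days before screening. The prohibited-medication item concerns concomitant use, which SAP 5.6.2 ties to the double-blind period. Compliance is judged from Baseline. Prior vibegron exposure (protocol exclusion criterion 36) is not on the list. Run-in vibegron falls between these windows.

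**The case against.** The best defence is context. The SAF bullet opens with double-blind medication, and the grouping sentence follows at once. Study day, exposure and TEAEs all run from the first double-blind dose. A programmer could naturally take the any-dose rule to mean double-blind doses, where it sensibly handles a placebo man given the wrong bottle after randomisation. That reading is reasonable, but the text does not say it, and the SAP itself has raised the run-in case one page earlier. If the intention were instead to count any exposure, run-in included, the TEAE and exposure windows would need to open earlier to match.

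A reader might go further and infer that this man's on-drug diary stays as baseline in the per-protocol analysis. The documents do not establish that. The list in SAP 3.2 is expressly not exhaustive, wrong treatment is a recognised major deviation, and exclusions are set in Protocol Deviation specifications that are not among the documents. It could also be argued that the prohibited-medication item reaches him, because protocol Section 10.6 bars beta-3 agonists as a class and SAP Table 6 places vibegron in that class.

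A reader might also infer bias in the efficacy comparison. An error made before randomisation does not by itself produce one. In addition, the primary model adjusts for baseline.

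Lastly, part of the listing remedy exists: SAP 7.1 already flags adverse events by onset period. What it lacks is a mark that the man was taking vibegron at the time. The two run-in listings in Table 11 use the run-in population, and if that is the Placebo Run-in Set, these men are left out of them.

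**Conclusion.** The safety classification point holds on the literal wording. A stated rule would put placebo-period data in the vibegron column for a case that the SAP itself foresees. It should be put as what the wording would do, since the narrower reading is open.

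The size is small in the full SAF: 0.01 to 0.18 percentage points of an event rate for 1 to 20 men, with both the counts and the rates assumed. It matters more in the Part 1 orthostatic set and the urodynamics sub-study, where one man is about 2.5% to 3% of an arm. The documents do not say whether any such man was in either set.

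The per-protocol part is a clarification only: no listed exclusion covers vibegron received in run-in, and no baseline exception is given. Severity is minor.

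**What to change.** 1. In SAP 3.1.4, write *any dose of double-blind vibegron* and *only double-blind doses of placebo*.
2. In the adverse event listings, flag run-in events of men given vibegron in run-in as vibegron-exposed, and make sure that these men appear there.
3. In SAP 3.2, state before unblinding that vibegron received in run-in excludes a man from the Per-Protocol Set (PPS), its incontinence version (PPS-I) and its urodynamics version (PPS-UES). The timing matters because SAP 3.1.7 fixes these sets before unblinding, whereas SAP 3.2 confirms wrong treatment only at unblinding.
4. Keep these men in the FAS as randomised, so the primary analysis does not change.

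The cost is a few words and one flag from the run-in drug records. The downside is that a few men change column in the safety tables and may leave the per-protocol sets.

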3.1.5. Urodyamics Evaluable Set

The Urodynamics Evaluable Set (UES) consists of all subjects in Part 2 who were randomized to the urodynamics sub-study, received at least one dose of double-blind study medication, had both Qmax and PdetQmax measurements at baseline and at least one Qmax or PdetQmax measurement at the post-baseline timepoint.

3.1.6. Full Analysis Set

The Full Analysis Set (FAS) population will serve as the primary population for the analysis of efficacy data in this trial. Since the endpoints related to incontinence only apply to subjects who meet the definition of incontinence at trial entry, it is necessary to have a separate FAS definition with an additional criterion to define the primary analysis population for incontinence endpoints.

The following FAS populations are defined in the study:

- **Full Analysis Set (FAS):** consists of all randomized subjects who took at least one dose of double-blind study medication and have at least one evaluable change from baseline micturition measurement. Subjects will be analyzed according to their randomized treatment, irrespective of premature discontinuation, according to the Intent-to-Treat principle.
- **Full Analysis Set for Incontinence (FAS-I):** consists of all randomized subjects with incontinence at baseline (as calculated from the baseline diary) who took at least one dose of double-blind study treatment and have at least one evaluable change from baseline urinary incontinence measurement.

Note that “subjects with urinary incontinence at baseline” are defined as meeting the following criteria based on the 3-day bladder diary completed by the subject during the Run-in period:

- An average of ≥ 8.0 micturitions per Diary Day. A “Diary Day” is defined as the time between when the subject gets up for the day each morning (i.e., the time the subject got up for the day yesterday to the time the subject got up for the day today; approximately a 24-hour period).
- An average of ≥ 1.0 urinary incontinence episodes per Diary Day

